12.2.10 Hearing and Language

Hearing Assessments

Hearing will be assessed by WIN assessment from the NIH Toolbox. The WIN outcome will be presented as the lowest signal-to-noise ratio (SNR) where at least 50% of words are correctly identified. The SNR from WIN will be summarized at the in-person visits by HIV status and compared to the normative population. The mean or median WIN SNR will also be compared between the PHIV and YAPHEU cohort using a Wilcoxon rank sum test. The association of HIV infection with WIN SNR will be further examined, both unadjusted and adjusted for possible confounders such as age, gender, aural history, upper respiratory issues, and/or recent exposure to loud noise, using generalized linear models. The changes in SNR over visits and a comparison of the changes between YAPHIV and YAPHEU cohorts will be summarized by descriptive statistics and explored by GEE models if appropriate. When sufficient literature support is available, SNR may be categorized to describe the severity of hearing loss.

WIN SNR will be used as a predictor for impairment in educational attainment and language, psychosocial, and cognitive functions. Depending on the data type of the variable of interest, logistic regression or multinomial regression models for categorical outcomes, and linear models or generalized linear models for continuous outcomes will be utilized to explore the effect of a hearing problem on language, psychosocial, education and cognitive outcomes separately. Effect modification by HIV status will be evaluated by including an interaction term between HIV status and WIN SNR. Successful transition to adult care will be a particular outcome of interest.

Another hearing assessment, the Hearing Threshold Test, may become available later during the conduct of this study. When and if it does, pure-tone thresholds will also be collected and analyzed. Hearing loss can be defined using the pure tone thresholds in various ways. First, pure-tone thresholds across the frequencies measured in the Hearing Threshold Test will be analyzed as continuous data. Second, three calculations of pure-tone average (PTA) will be completed. A low-frequency PTA will be the average of thresholds at 500, 1000, and 2000 Hz; a high-frequency PTA will be the average of thresholds at 4000, 6000, and 8000 Hz; and a clinical PTA will be the average of 500, 1000, 2000, and 4000 Hz will be determined. The clinical PTA will allow for these data to be compared to hearing data in the earlier AMP protocol. A participant with a PTA greater than 20 dB will be defined as having a hearing loss. The pure-tone thresholds of each frequency will then be summarized and compared by HIV status and to the normative population. Association between PTA and WIN SNR will be explored by Pearson or Spearman's rank correlation, and WIN SNR will also be summarized by hearing loss status. The prevalence of hearing loss by each definition will be estimated at each time point. The odds ratio for hearing loss between cohorts will be estimated adjusting for possible confounders. Any changes in hearing loss status over time will also be explored. Hearing loss defined using the clinical PTA will also

be used as a predictor for impairment in educational attainment and language, psychosocial, and cognitive functions.

Language Development

Language development will be assessed on the CELF-4. This test is normed through age 21 years and 11 months, generating standard scores benchmarked to age. The CELF-4 will be administered to participants through 21 years of age (See Section 9.4 for administration details).

Language impairment will be defined as one standard deviation or more below the reference mean, and severe language impairment as two standard deviations below the reference mean. Relevant aggregated scores may be developed for grammar (Recalling Sentences and Formulated Sentences) and vocabulary (Word Classes – Receptive, Word Classes – Expressive and Word Definitions) separately. The prevalence of language impairment will be estimated by HIV infection status, and compared between YAPHIV and YAPHEU, and to the normative population (16% by definition). Individual variation in language development in the full available age range, 5-30 years, is validly measured by raw score performance on the Recalling Sentences and Formulated Sentences subtests administered throughout this age range; in addition, Word Classes Receptive and Word Classes Expressive for ages 9-30, and Word Definitions for the full age range. Summative raw scores per subtest are also available. In addition, item level data needed for these five subtests for the development of trait-level scores will be collected for investigation of changes over time.

Using the CELF-4 test results, risk for language impairment relative to age expectations as a binary outcome will be examined, and predictors of language impairment will be examined using logistic regression models comparing YAPHIV to YAPHEU, adjusting for potential confounders. Within YAPHIV, linear regression models will be fit to evaluate associations of grammar and semantic outcomes with HIV disease severity, and ARV regimens. In addition, multiple logistic regression will be applied to study the association between language impairment and viral load, CD4 count, and CDC class. For the subset with previous assessments in AMP study, the effect of cART on change in language impairment will be investigated by numbers of regimens, type, and duration of cART. Specific ARV drugs for which associations with language outcomes have been previously observed, such as atazanavir, will be studied.

For AMP Up participants with previous language assessments using the CELF-4 at younger ages, availability of a second or third CELF-4 language assessment will allow us to examine consistency of performance relative to age expectations over multiple measurement; evaluate predictors of incident language impairment or resolution of prior language impairment, and evaluate predictors of age-normed language scores over time. Approximately 345 participants with PHIV and 193 participants with PHEU from the AMP study had at least one CELF-4 assessment between the age of 7 to 16 years, and around 80% of these participants had two previous CELF-4 assessments in AMP. Approximately 280 of these participants enrolled into AMP Up are monolingual and younger than 22 years old by the Year 3 visit. The change of CELF scores by HIV status will be studied, adjusting for age, time from the previous assessment(s) in AMP, and other confounders. GEE or mixed effect models will be used to account for the correlation in outcomes measured over time on the same participant. When feasible, growth curve models will also be fitted to explore the pattern of changes over time. Dependent variables are determined by psychometric properties of the CELF-4. For ages 5-21 years, the Expressive Language Total Standard Score is comparable, as are the subtests Recalling Sentences and Formulated Sentences; in addition, for 9-21 years, the subtests Word Classes- Receptive, Word Classes - Expressive and Word Definitions are valid for comparison of the last two times of measurement.

Association between language impairment and hearing and cognitive impairments will be measured using logistic regression models to obtain odds ratios, adjusting for possible confounders. Logistic, multinomial, or generalized linear regression models will be applied to study language impairment as a predictor for socio/emotional, education and employment outcomes separately, adjusting for hearing and cognitive impairments and other possible confounders.

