2.2.10 Hearing and Language

Specific Aims:

- To assess changes in language acquisition from childhood to young adulthood in YAPHIV and YAPHEU and, among YAPHIV, the association of these changes with HIV disease severity and ARV exposure.
- To determine how language abilities and hearing in adolescence predict employment status, educational status, reading abilities and life satisfaction in young adulthood.
- To evaluate hearing sensitivity of YAPHIV and YAPHEU, and to evaluate the associations of ARV exposure and HIV disease severity with these outcomes.

Hypotheses:

- Language impairments will be stable over time in both YAPHIV and YAPHEU.
- Among YAPHIV, ARV effects will differ by ARV type, age, and specific language outcomes.
- Young adults with language or hearing impairment will be at increased risk of negative social, academic, and employment outcomes.

- Compared to YAPHEU, YAPHIV will have poorer hearing and language outcomes, which are associated with HIV disease status and ARV exposure.

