4.1 YAPHIV Cohort

4.1.1 Inclusion Criteria

To be considered eligible for enrollment, an individual must meet all the criteria listed below:

- Has perinatal HIV infection as documented in the medical record.
- Is at or beyond their 18th birthday at the time of informed consent.
- Is willing to provide access to existing medical records.
- At least one of the following is true:
 - Previously enrolled in any of the studies included on the list of approved studies (see list of approved studies meeting the eligibility requirement for enrollment into AMP Up on page 15), or
 - Available medical record documentation* since early childhood, if possible, but no later than 12 years of age. Medical records must also be available starting no later than 2 years after HIV diagnosis and include:
 - ART exposure history,
 - Opportunistic infection prophylaxis exposure history,
 - Viral load and CD4 cell count history, and
 - Major medical events history.

*Medical record documentation should consist of all existing records from when the participant entered care with no gaps in existing records of more than 12 months.

- Is willing to participate and provide legal written consent.

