9.4 Language and Hearing Assessments

The CELF-4 is a standardized test to be administered to those participants previously enrolled in AMP and who have completed at least one previous CELF-4 while in AMP. Only those participants in AMP who had at least one CELF completed in AMP will be administered the CELF-4 in AMP Up. The CELF-4 should be administered at the Entry visit for those participants who will be 22 years or older by the time of their Year 3 visit. All others will have the CELF-4 administered at the Year 3 visit. Clinical site staff can obtain a list of PIDs for participants that meet the criteria for CELF administration from the AMP Up CELF-4 Visit Calculator located on the Frontier Science PHACS Portal. The CELF-4 will be administered by centrally trained PHACS staff and does not require administration by a psychologist. Subtests include Recalling Sentences, Formulated Sentences, Word Classes-Receptive, Word Classes-Expressive, and Word Definitions. The assessment incorporates culturally appropriate contexts and visual stimuli. Updated norms are based on a diverse standardization sample of 2,650 participants that reflect the updated 2000 U.S. Census, including children with identified conditions and diagnosed language disorders (Semel et al., 2003). The Core Language and Expressive Language composite scores will be analyzed.

Participants will be screened at the Entry, Year 3, 6, 9, and 12 visits for hearing problems using the WIN hearing test from the NIH Toolbox. WIN measures a person's ability to recognize single words presented amid varying levels of background noise to assess how much difficulty a person might have hearing in a noisy environment. A recorded voice instructs the participant to listen to and then repeat words. The task becomes increasingly difficult as the background noise gets louder. See Section 9.3 for more information about the NIH Toolbox.

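### The aim asks what adolescent hearing predicts, but every hearing predictor fixed in Section 12.2.10 is measured at age 18 or older

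*Protocol*

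**What the plan says.** The aim, in Section 2.2.10 and repeated in the Study Abstract, is: "To determine how language abilities and hearing in adolescence predict employment status, educational status, reading abilities and life satisfaction in young adulthood". The paired hypothesis in the same section is framed differently: "Young adults with language or hearing impairment will be at increased risk of negative social, academic, and employment outcomes".

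The hearing analysis in Section 12.2.10 states: "WIN SNR will be used as a predictor for impairment in educational attainment and language, psychosocial, and cognitive functions". Section 9.4 gives the timing: "Participants will be screened at the Entry, Year 3, 6, 9, and 12 visits for hearing problems using the WIN hearing test". Entry to AMP Up requires that a YAPHIV participant "Is at or beyond their 18th birthday at the time of informed consent", and Section 4.2.1 sets the same age for YAPHEU.

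A second measure is conditional: "Another hearing assessment, the Hearing Threshold Test, may become available later during the conduct of this study". If it does become available, hearing loss by clinical pure-tone average (PTA) will be used as a predictor of the same outcomes as WIN. Of the AMP data the section says only: "The clinical PTA will allow for these data to be compared to hearing data in the earlier AMP protocol".

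For language, Section 12.2.10 reports that about 345 PHIV and 193 PHEU participants "had at least one CELF-4 assessment between the age of 7 to 16 years". It plans models with language impairment as a predictor of socio-emotional, education and employment outcomes.

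**The concern.** The aim separates two life stages: hearing is to be taken from adolescence, and outcomes from young adulthood. The planned hearing predictor belongs to the second stage. A model with adult WIN as predictor can describe how adult hearing relates to adult outcomes, but it cannot say what adolescent hearing foretells.

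Nor is WIN simply a later reading of what AMP measured. It scores recognition of spoken words against noise, whereas the AMP comparison in Section 12.2.10 runs through pure-tone thresholds. The section treats the correlation between PTA and WIN as something to be explored, so the plan does not assume that they are interchangeable.

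If the plan is followed as written, the WIN models could be reported under this aim and read as prediction from adolescence, while the AMP hearing data that could address the question go unused for it.

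**Working it through.** No power or sample-size figure is involved. The check sets the aim against each place where hearing enters an analysis.

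**Age at each hearing predictor**

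- WIN: the first is at Entry (Year 0). Minimum age = 18 + 0 = 18 years. Later scheduled tests (Years 3, 6, 9, 12) come at higher ages.
- Clinical PTA: it comes from a test that may be introduced during AMP Up, so the minimum age is again 18.
- AMP hearing: the only measure that could date from adolescence. Section 12.2.10 uses it for comparison and in no model as a predictor.

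Planned hearing predictors: 2. Measured before age 18: 0.

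**Other roles of hearing in Section 12.2.10.** Hearing is an outcome compared by HIV status. Hearing impairment is examined for association with language impairment, and it is an adjustment variable in the models where language impairment is the predictor. None of these makes adolescent hearing a predictor of the aim's outcomes.

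**Could another section supply the analysis?**

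- Section 12.0 says most analyses will draw on historical data. It refers to earlier cohorts with detailed ART exposure information and names no hearing measure.
- Section 12.2.9 plans logistic and linear models for adult functioning and quality of life, and the aim in Section 2.2.9 includes adolescent factors. Hearing is not named in either.
- Where AMP-era data are meant, the plan says so: caregiver information in Section 12.2.6, adolescent trajectories in Section 12.2.7, and earlier language assessments in Section 12.2.10. For hearing it names WIN.

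**Outcomes**

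| Outcome in the aim | Named for the hearing predictors in 12.2.10? |
|---|---|
| Employment status | No |
| Educational status | Yes, as impairment in attainment |
| Reading abilities | No; language function is named |
| Life satisfaction | Not by name; psychosocial function could include it |

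**Ceiling on the usable subset.** Section 1.1 counts 294 YAPHIV and 124 YAPHEU who had enrolled from AMP. 294 + 124 = 418, against a target of 650 + 200 = 850, and 418 / 850 = 49%. This counts all AMP-origin enrollees at the time of writing, not those with hearing data. That number, and the ages at which AMP hearing was tested, are not given.

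**The case against.** The strongest reply is that the WIN sentence is not wrong in itself. The paired hypothesis concerns young adults who have an impairment, and adult WIN suits it. On that view the fault lies between the aim and its hypothesis, and rewording the aim would cure it. This stands as a description of the WIN model, and it is why rewording is kept below as the fallback. It does not give the aim an analysis.

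A reader might infer more than the protocol supports, in three ways.

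- **That prediction from adolescence is tested nowhere, language included.** This does not hold. A model with language impairment as predictor is planned, in the same section that describes CELF-4 scores from ages 7 to 16. Which assessment wave it uses is not stated, but that leaves adolescent prediction open rather than excluded, and the choice is a detail that a statistical analysis plan can settle.
- **That WIN has no lead time over the outcomes.** This does not hold either. Nothing pairs WIN with outcomes from the same visit. WIN at Entry could precede the Year 1 survey by 1 year (1 - 0) or Year 3 Toolbox scores by 3 years (3 - 0). The exposure would still be adult, which is the point that survives.
- **That the 418 AMP-origin participants could all be analysed at once.** The protocol does not say how many of them had a hearing test.

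The point on outcomes is also limited. Life satisfaction can be read into psychosocial function, and a generous reader could put reading under language. Employment has no such cover for the hearing predictors, although it is named for the language predictor.

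**Conclusion.** The concern holds for hearing only. The aim specifies hearing in adolescence; both hearing predictors in Section 12.2.10 are adult measures, and no planned model uses AMP hearing as a predictor. The hearing half of this aim therefore has no matching analysis, and employment and reading are not named as outcomes of the hearing predictors.

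This is a mismatch between passages of the protocol itself, not a detail left for later: the predictor is named, and it belongs to the wrong life stage for the aim. Its reach is half of one domain aim. The primary objectives, the WIN comparisons by HIV status and the paired hypothesis are untouched. It is worth correcting because the protocol indicates that AMP hearing data exist, so the study may be able to answer the question it poses.

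The conclusion rests on two readings: that adolescence in the aim means before AMP Up entry at 18, and that the general remark in Section 12.0 on historical data does not silently extend to hearing. Whether the added analysis is feasible depends on the unstated number and ages of the AMP hearing tests.

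**What to change.** In Section 12.2.10:

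1. Add a model with AMP hearing, PTA-based and measured before age 18, as predictor of employment, educational status, reading and life satisfaction at AMP Up visits. Restrict it to AMP-origin participants with AMP hearing data, and say which score represents reading.
2. State, as a clarification, that the pre-18 AMP CELF-4 is the language predictor for this aim.
3. Keep the WIN models as analyses of adult hearing that address the paired hypothesis, and do not report them as prediction from adolescence. Any lag between WIN and outcome can be described as such.
4. Before committing to step 1, count the enrolled participants with AMP hearing data and tabulate their ages at testing. If there are too few, reword the aim in Section 2.2.10 and the Study Abstract to adult hearing.

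This needs no new data collection. It costs text changes and analysis time. The drawback is that the added model uses only the AMP-origin subset, so it will be less precise than the full-cohort WIN models and will describe only participants who came from AMP.

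### Section 12.2.10 names only impairment cut at 1 SD for the cross-sectional cohort comparison of language and for language as a predictor; the age-normed CELF-4 standard scores should be added to both

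*Protocol*

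**What the plan says.** Section 12.2.10 (Language Development) sets the cut: "Language impairment will be defined as one standard deviation or more below the reference mean". Impairment prevalence is then compared between the cohorts and with a normative 16%. From the CELF-4 results, "risk for language impairment relative to age expectations as a binary outcome will be examined", and the adjusted cohort comparison is also binary: "predictors of language impairment will be examined using logistic regression models comparing YAPHIV to YAPHEU, adjusting for potential confounders". Linear models of grammar and semantic scores follow, but only within YAPHIV.

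For adult outcomes, the same section plans logistic, multinomial or generalized linear models to "study language impairment as a predictor for socio/emotional, education and employment outcomes separately".

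Other parts of the protocol treat language as a score:
- Section 9.4: "The Core Language and Expressive Language composite scores will be analyzed".
- Section 2.2.10, prediction aim: "To determine how language abilities and hearing in adolescence predict employment status, educational status, reading abilities and life satisfaction in young adulthood".
- Section 12.2.10, longitudinal part: change in CELF scores by HIV status and predictors of age-normed scores over time, using GEE, mixed or growth curve models.

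**The concern.** Section 2.2.10 hypothesises that YAPHIV have poorer language outcomes than YAPHEU, which is a statement about level. It also aims to learn how language abilities predict adult outcomes. For both questions, the cross-sectional and predictor models in Section 12.2.10 name only a yes/no version of a measured score. A participant just below the cut counts the same as one far below it, and a participant just above it counts the same as one well above the mean.

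Comparable measures are handled differently. In the same section, the WIN signal-to-noise ratio is compared between cohorts on its own scale and used uncut as a predictor. Section 12.2.6 evaluates cognitive outcomes both as continuous and as binary measures. No reason is given for treating language otherwise.

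At stake is a real cohort difference in level, or a real link between language and employment or education, being missed because of the scale chosen.

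**Working it through.** **Inputs**
- Cut at z = -1 and normative rate 16% (Section 12.2.10); exact normal tail 0.159.
- Impairment rate in AMP children: 24% + 11% = 35% (Section 1.1.11, which describes the two groups as equivalent in risk).
- Power 80%, alpha 0.05 (Section 12.1.1), taken as two-sided.
- Assumptions: normal scores, equal SD, a pure mean shift, and 35% as a plausible YAPHEU rate at the same cut.

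**1. The protocol's own figures.** Detectable difference = (1.960 + 0.842) × sqrt(1/n1 + 1/n2).
- 650 vs 200: 2.802 × sqrt(1/650 + 1/200) = 2.802 × 0.0809 = 0.227 SD.
- 415 vs 101: 2.802 × sqrt(1/415 + 1/101) = 2.802 × 0.1110 = 0.311 SD.

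Both match Section 12.1.1; the noncentral t gives power of 80.1% and 79.9%. These are whole-cohort sizes. The protocol gives no power for CELF-4, so they serve below only as a worked example.

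**2. Efficiency of the cut.** Relative efficiency = φ(z)² / [p(1 − p)], where p is the proportion impaired and z its normal quantile.
- p = 0.159: 0.2420² / 0.1335 = 0.44.
- p = 0.35: 0.3704² / 0.2275 = 0.60.

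Power after the cut, starting from 80%, is Φ(2.802 × sqrt(efficiency) − 1.96): 46% at 0.159 and 59% at 0.35. Sample size does not enter.

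**3. Cohort comparison, finite samples.** Shifted rate p1 = Φ(Φ⁻¹(p0) + d). Power = Φ[(p1 − p0 − 1.96 × SE0) / SE1], where SE0 uses the pooled proportion and SE1 the separate proportions. For 415 vs 101, d = 0.311:
- p0 = 0.159: p1 = 0.246, SE0 = 0.0466, SE1 = 0.0421, power 45.8% (simulation of 5000 runs: 45.9%).
- p0 = 0.35: p1 = 0.471, SE0 = 0.0552, SE1 = 0.0534, power 59.2% (simulation: 60.4%).

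Other sizes, each with d set for 80% power on the score:

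| YAPHIV / YAPHEU | d (SD) | Cut, 16% | Cut, 25% | Cut, 35% |
|---|---|---|---|---|
| 650 / 200 | 0.227 | 46% | 54% | 59% |
| 415 / 101 | 0.311 | 46% | 54% | 59% |
| 180 / 100 (assumed) | 0.351 | 48% | 56% | 60% |
| 197 / 83 (assumed) | 0.368 | 47% | 55% | 60% |

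A Wald test on the log odds ratio for 180 / 100 gives 47% and 59% at the two ends. For 415 / 101, the difference detectable with 80% power rises from 0.311 SD to 0.39 SD (35%) or 0.45 SD (16%).

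**4. Language as predictor.** Cutting the predictor multiplies its correlation with a continuous outcome by φ(z)/sqrt[p(1 − p)]: 0.66 at 16% and 0.78 at 35%, where p is now the proportion impaired in the analysed sample. With N = 280, the correlation giving 80% power is tanh(2.802/sqrt(277)) = 0.167; Fisher-z power after the cut is 45% and 58%. With N = 516 the correlation is 0.123 and power is 46% and 58%. The loss is again the same at either size.

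**The case against.** **The scores are analysed elsewhere.** A reader might infer that language differences by HIV status are studied only through the cut, so that this power is lost to the study as a whole. The documents do not support that. Section 12.2.10 plans score models over time, and CELF-4 goes only to people with an earlier AMP assessment (Section 9.4), so those models draw on the same participants. A mixed model could also yield an HIV main effect. What remains is that the only HIV-status contrast named there is change. Section 2.2.10 expects impairments to be stable, so the cohorts could differ in level without differing in change. The longitudinal models do not touch the predictor question.

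**The cut serves stated hypotheses.** Section 2.2.10 words two hypotheses in terms of impairment: stability over time, and higher risk of negative adult outcomes. The comparison with the 16% norm needs the cut too. This stands, so the impairment models should not be reduced to description.

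**The sample is not simply small.** One might read the approximately 280 in Section 12.2.10 as the whole language sample. That count covers monolingual AMP Up enrollees under 22 by Year 3. Section 9.4 also tests, at Entry, those who will be 22 or older by then, and adolescent language was measured in AMP, where about 345 + 193 had a CELF-4. Absolute detectable differences therefore cannot be pinned down; the relative loss can.

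**The larger loss may not apply.** Section 1.1.11 reports elevated and equivalent risk in both groups, which favours the 35% end.

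**Residual confounding.** Nothing in the protocol makes dichotomised language an adjustment variable, so no such bias can be claimed.

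**Conclusion.** The point holds for two named sets of models: the cross-sectional YAPHIV-versus-YAPHEU comparison, and language as a predictor of socio/emotional, education and employment outcomes. In each, the cut discards about 40% of the information at a 35% impairment rate and about 56% at 16%. For the cohort comparison, power falls from 80% to about 59% or about 47% respectively; for the predictor, to about 58% or 45%. The 35% figures are the more plausible on the protocol's own account.

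These are conditional figures, resting on normal scores, a mean shift (or a linear association, for the predictor) and an effect chosen to give 80% power on the score. They contradict no power claim in the protocol. The impairment analyses are not wrong; they are an inefficient sole choice for questions about level and ability when the score is already in hand.

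**What to change.** In Section 12.2.10:

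1. Add the age-normed Core Language and Expressive Language standard scores as a continuous outcome of the cross-sectional YAPHIV-versus-YAPHEU comparison, by linear regression or GEE with the same confounders as the logistic model.
2. Add the standard score as a continuous predictor in the socio/emotional, education and employment models.
3. Keep the impairment prevalence, the comparison with the 16% norm and the impairment models, which test the impairment-worded hypotheses in Section 2.2.10.

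The cost is a sentence or two of text and a few extra models on data already collected, with no new visits or participants. A score difference is less directly clinical than an impairment rate, but the impairment rate would still be reported beside it.
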